7.3 Center Pooling

Data from all geographies and active centers will be included in the analyses; there are no planned poolability analyses.

7.4 Handling of Missing, Unused, and Spurious Data and Dropouts

Every effort will be undertaken to minimize missing data. Missing (accidentally, due to withdrawal, missing follow-up or loss to follow-up, etc.), unused and spurious data will remain identifiable in the database. For time-to-event outcomes, dropouts will be censored at the time of discontinuation, consistent with the Kaplan-Meier approach. Unless otherwise specified, all analyses will be based on available data and missing data will not be imputed. The number of subjects included in each analysis will be reported so that the reader can assess the potential impact of missing data.

In the case of partial dates, unknown portions will be imputed for the purposes of analysis. If only the month and year are known, the event or assessment will be analyzed as if it occurred on the 15th of the known month. If only the year is known, the event or assessment will be analyzed as if it occurred on June 30th of the known year. Imputation of partial dates is subject to the restriction that pre-implant events must occur between the date of informed consent and the date of implant and post-implant events must occur after the date of implant.

7.5 Adjustments for Multiple Comparisons

The study is descriptive without formal hypothesis testing; methods for multiplicity adjustment are not applicable.

7.6 Demographic and Other Baseline Characteristics

Baseline demographics and clinical variables will be summarized descriptively for the attempted implant analysis set. Data will be summarized with standard descriptive summary statistics, including counts and percentages for categorical variables, and mean, standard deviation, median, first and third quartiles, minimums and maximums for continuous variables.

7.7 Treatment Characteristics

Implant procedure data will be summarized for the attempted implant analysis set. Data will be summarized with standard descriptive summary statistics, including counts and percentages for categorical variables, and mean, standard deviation, median, first and third quartiles, minimums and maximums for continuous variables.

7.8 Interim Analyses

An initial analysis is planned when the first 50 to 75 implanted subjects have completed his/her 6 month follow-up; however initial analyses may be performed earlier if enrollment is slower than expected. Initial analyses will assess all safety and efficacy endpoints based on available data. The analysis will be descriptive and no formal interim analyses are planned for the purpose of early stopping or sample size re-estimation.

7.9 Evaluation of Objectives

7.9.1 Safety Endpoints

The following safety endpoints are defined and will be analyzed:

1. All-cause and cardiovascular mortality at 30 days and 6 months
2. All stroke (disabling and non-disabling) at 30 days and 6 months
3. Myocardial infarction (periprocedural and spontaneous) at 30 days and 6 months
4. Acute kidney injury at 30 days and 6 months
5. Major vascular complications at 30 days and 6 months
6. Life-threatening bleed at 30 days and 6 months
7. New permanent pacemaker implantation (PPI) at 30 days and 6 months
8. New intraventricular conduction delays at 30 days and 6 months
9. New-onset atrial fibrillation at 30 days and 6 months
10. Valve-related dysfunction requiring repeat procedure at 30 days and 6 months

Safety endpoints will be adjudicated by the Clinical Events Committee (CEC) and analysis will be based on data collected on the CEC adjudication form. Safety endpoints will be analyzed with Kaplan-Meier survival analysis methods according to Section 7.2. Safety endpoints will be analyzed using the Attempted Implant population.

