6.2.2 Exclusion Criteria

If any of the following exclusion criteria are present, the prospective subject is not eligible for implantation:

1. Age < 65 years
2. Class I indication for cardiac surgery
3. Very severe aortic stenosis, defined as $V_{\text{max}} \geq 5 \text{ m/sec}$, or mean gradient $\geq 60 \text{ mmHg}$
4. Bicuspid, unicuspid, or quadracuspid aortic valve
5. Contraindication for placement of a bioprosthetic valve
6. A known hypersensitivity or contraindication to any of the following that cannot be adequately pre-medicated:
 - Aspirin, heparin, or bivalirudin
 - Ticlopidine and clopidogrel
 - Nitinol (titanium or nickel)
 - Contrast media

7. Blood dyscrasias as defined: leukopenia (WBC < 1000 mm³), thrombocytopenia (platelet count <50,000 cells/mm³), history of bleeding diathesis or coagulopathy, or hypercoagulable states
8. Ongoing sepsis, including active endocarditis
9. Any percutaneous coronary or peripheral interventional procedure within 30 days prior to date of qualifying echocardiogram
10. In need of and suitable for coronary revascularization per Heart Team
11. Chronic obstructive pulmonary disease (GOLD stage 3 or higher)⁵⁷
12. Placement of cardiac resynchronization device within 90 days of qualifying echocardiogram
13. Symptomatic carotid or vertebral artery disease or successful treatment of carotid stenosis within 70 days of qualifying echocardiogram
14. Heart failure event or hospitalization within 14 days prior to qualifying echocardiogram
15. Cardiogenic shock manifested by low cardiac output, vasopressor dependence, or mechanical hemodynamic support
16. Recent (within 60 days of qualifying echocardiogram) cerebrovascular accident (CVA) or transient ischemic attack (TIA)
17. Child-Pugh class C liver cirrhosis
18. Gastrointestinal (GI) bleeding that would preclude anticoagulation
19. Subject refuses a blood transfusion
20. Severe dementia (resulting in either inability to provide informed consent for the study/procedure, prevents independent lifestyle outside of a chronic care facility, or will fundamentally complicate rehabilitation from the procedure or compliance with follow-up visits)
21. Estimated life expectancy of less than 24 months due to associated non-cardiac co-morbid conditions
22. Other medical, social, or psychological conditions that in the opinion of the investigator precludes the subject from appropriate consent or adherence to the protocol required follow-up exams

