13.3.2 General Procedures

- Protocol-driven exams should be performed by designated individuals delegated by the site PI
- Subject's blood pressure and weight should be recorded at each visit. Blood pressure should be taken with the subject sitting in a chair after resting for 5-10 minutes. Subject's weight can be taken with shoes off or on.⁶
- The subject's ID number and exam interval should be annotated on the image.
- A simultaneous ECG with a clearly defined R-wave should be displayed on all clips
- Digital cine clips should be a minimum of two cardiac cycles
- To minimize inter-vendor and inter-software variation in GLS measurements, serial assessments should be performed using the same vendor's equipment and software to the extent practical.
- Color Doppler images for assessment of prosthetic regurgitation should be obtained at a minimum frame rate of 20 Hz through optimization of sector width and depth settings.
- Still frames of measured variables should be captured. In addition, still frames of spectral Doppler tracings without the measurements should be captured to facilitate analysis by the Echo Core Lab. Still frames of spectral and tissue Doppler tracings should contain a minimum of 3 cardiac cycles for subjects in sinus rhythm, and a minimum of 5 cardiac cycles for subjects in atrial fibrillation (two sequential frames per variable may be necessary).
- Spectral and tissue Doppler waveforms should be recorded at a minimum sweep speed of 50 mm/sec.
- Exams will be transmitted to the Echo Core Lab via web-based picture archiving and communication system. Details of the image transmission process for each site will be established during site initiation process.

⁶ Weight can be taken from the clinical assessment exam. Blood pressure should be taken within 5-10 minutes before or after the echo exam.

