The primary objectives of this feasibility study are as follows:

1. Characterize the spectrum of cardiac function, symptomology, and severity of aortic stenosis in the study populations,
2. Estimate event rates for potential safety and effectiveness endpoints to be evaluated in pivotal studies for the proposed patient populations, and
3. Evaluate the effect of TAVR on cardiac function, functional capacity, effort tolerance, and patient-reported quality of life in the study populations.

The study objectives and associated endpoints are intended to fully characterize the spectrum of aortic stenosis (AS) severity, left ventricular (LV) function, and symptomology of patients with moderate

symptomatic and severe asymptomatic AS, provide information on event rates for pivotal sample size estimations, and refine the entrance criteria for future pivotal studies. The full list of protocol defined endpoints are detailed in Section 7.9. Of the protocol defined endpoints, the following key study endpoints have been identified:

Key Safety Endpoints:

- All-cause mortality at 30 days and 6 months
- All stroke (disabling and non-disabling) at 30 days and 6 months
- Valve-related dysfunction requiring repeat procedure at 30 days and 6 months
- New permanent pacemaker implant (PPI) at 30 days and 6 months

Key Efficacy Endpoints:

- Cardiovascular and heart failure hospitalizations at 30 days and 6 months
- Heart failure events at 30 days and 6 months
- Change in Kansas City Cardiomyopathy Questionnaire (KCCQ) at 6 months
- Change in Six-Minute Walk Test (6MWT) at 6 months
- Change in cardiac function by echo (LVEF, Peak GLS, E:e') at 6 months

5. Investigation Plan

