7.1.3 Analysis Sets

The enrolled population will consist of all subjects who signed the informed consent. The following analysis sets are defined within the enrolled population:

1. **Attempted Implant set:** The attempted implant data set will include all subjects with an attempted implant procedure, where an attempted implant is defined as when the subject is brought into the procedure room and any of the following have occurred: anesthesia administered, vascular line placed, Transesophageal echocardiography (TEE) placed or any monitoring line placed. Day 0 is the date of first attempted procedure.
2. **Implanted set:** The implanted data set includes all subjects with an attempted implant where the study device is implanted, defined as when the transcatheter aortic valve (TAV) is fully released from the delivery catheter system (DCS). Day 0 is the date of first attempted procedure.

In general, the primary analysis of safety, clinical outcomes, and quality of life (QoL) outcomes will be performed using the Attempted Implant analysis set and primary analysis of echo-related outcomes will be performed using the Implanted analysis set. The primary analysis population for each endpoint are detailed in Section 7.9. Analysis performed using analysis sets other than the primary would be considered supportive.

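### New pacemaker, new-onset AF and new conduction delay are estimated only in all attempted subjects; a rate among subjects free of the condition at baseline should stand beside it

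*SAP*

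**What the plan says.** SAP 7.9.1 lists ten safety endpoints. Three are restricted to new occurrences: "New permanent pacemaker implantation (PPI) at 30 days and 6 months", "New intraventricular conduction delays at 30 days and 6 months" and "New-onset atrial fibrillation at 30 days and 6 months". The first is also a key safety endpoint in SAP section 4. All ten share one analysis set: "Safety endpoints will be analyzed using the Attempted Implant population". Protocol 10.4 says the same.

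Membership of that set depends only on the procedure having been started: "The attempted implant data set will include all subjects with an attempted implant procedure" (SAP 7.1.3). SAP 7.2 gives one Kaplan-Meier rule for every time-to-event outcome. A subject without an event stays in the risk set until last contact, and no endpoint has its own risk set.

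The inclusion and exclusion criteria (protocol 6.2.1 and 6.2.2) exclude neither AF nor conduction delay. The only criterion about a rhythm device is "Placement of cardiac resynchronization device within 90 days of qualifying echocardiogram", which leaves an existing pacemaker eligible. Protocol 13.8.1, which holds the safety definitions, defines none of the three endpoints.

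**The concern.** A subject who arrives with a pacemaker cannot receive a new one in the sense of the endpoint, and a subject with known AF cannot have new-onset AF. Under the plan both enter the Kaplan-Meier denominator at day 0 and are counted as event-free throughout. The estimate then mixes two things: the risk in those who can have the event, and the share of this sample that cannot.

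This matters because of how the rates will be used. The second primary objective is to estimate event rates for endpoints of later pivotal studies, and protocol 5.2 names pivotal sample-size estimation as a use. A planner who takes the all-attempted rate also takes over this sample's baseline prevalence. If the pivotal study counts only subjects free of the condition, or recruits with a different prevalence, the borrowed rate will not fit.

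**Working it through.** **No figure to reproduce.** The plan gives no expected rate for these endpoints. It states that the 75 subjects were not derived statistically (protocol 10.7, SAP 6).

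**Inputs from the documents.** N = 75; Kaplan-Meier at days 30 and 183; 95% limits on the log-log scale with the Greenwood standard error (SAP 7.2).

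**Assumed inputs.** The baseline prevalence π, the at-risk risk r and the event count below are not in the documents. They serve only to show the range.

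**Step 1, the identity.** If a share π cannot have the event and censoring does not depend on baseline status, then

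all-attempted rate = (1 − π) × r, so at-risk rate ÷ all-attempted rate = 1 ÷ (1 − π).

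| π (assumed) | 1 ÷ (1 − π) | Reported rate if r = 15% |
|---|---|---|
| 0% | 1.00 | 15.0% |
| 5% | 1.05 | 14.25% |
| 10% | 1.11 | 13.5% |
| 20% | 1.25 | 12.0% |
| 30% | 1.43 | 10.5% |

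**Step 2, check with censoring.** A simulation of 3,000 studies of 75 subjects used π = 20%, r = 15% by day 183 and about 5% loss. The mean Kaplan-Meier rate at day 183 was 11.9% in all subjects and 14.9% in those at risk. The identity gives 0.80 × 15% = 12.0%.

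**Step 3, on the scale of this study.** Take 9 events among 75 subjects (assumed) and no censoring. With x events in n subjects, S = 1 − x/n. The standard error of log S is √[x ÷ (n(n − x))], and the limits for the event rate are 1 − S^exp(±1.96 × SE ÷ |log S|).

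| Affected at baseline | At-risk n | Rate | 95% limits |
|---|---|---|---|
| 0 (as planned) | 75 | 9/75 = 12.0% | 6.4 to 21.8% |
| 4 | 71 | 9/71 = 12.7% | 6.8 to 22.9% |
| 8 | 67 | 9/67 = 13.4% | 7.2 to 24.2% |
| 15 | 60 | 9/60 = 15.0% | 8.1 to 26.8% |
| 22 | 53 | 9/53 = 17.0% | 9.2 to 30.1% |

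The direction is the same for every π above zero. The size runs from trivial to material.

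**The case against.** **The all-attempted rate is a legitimate quantity.** It is the share of treated subjects who have the event, and a pivotal study that counts events in all treated subjects would need exactly that. This stands. A reader might infer that the planned rates are wrong or cannot be transferred at all. The documents do not support this: the plan never claims to estimate the conditional risk, and under similar eligibility the prevalence may travel with the rate.

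**Not every affected subject is immune.** A reader might treat all three endpoints alike. For conduction delay that fails, because a subject with one defect can develop another. Protocol 13.8.3 lists several separate conduction disturbances and, for hospitalizations, counts worsening as well as new ones. The gap for this endpoint is first a missing definition.

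**Evidence of AF at baseline.** The echo instructions ask for "a minimum of 5 cardiac cycles for subjects in atrial fibrillation" (protocol 13.3.2), and a reader might take this as proof that subjects with AF are expected at entry. It is not. The rule covers every echo from baseline to five years and would be needed for AF that starts after implant. The support is only that the criteria contain no exclusion.

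**The effect may be small.** With 4 of 75 affected, 12.0% becomes 12.7%, against planned limits of 6.4 to 21.8%. Nothing in the documents supports 20 or 30% for a prior pacemaker. This stands, and so the size must be left open.

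**Much is already reported.** SAP 7.2 reports numbers at risk and with events, SAP 7.6 summarizes baseline variables, and SAP 7.1.3 and 7.9.4 allow supportive and extra subgroup analyses. A reader could rescale if baseline pacemaker and AF status were tabulated, but neither document commits to that. Adjudication by the Clinical Events Committee, under a charter not included here, settles which events count; SAP 7.9.1 still sets the denominator.

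**Conclusion.** The point holds as a missing second denominator. It does not show that the planned estimate is invalid. SAP 7.9.1 has no rule for subjects with the condition at baseline, and the criteria admit them. The all-attempted rate is therefore lower than the risk among subjects who can have the event by the factor (1 − π), and equal to it only if nobody is affected.

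The size cannot be computed from the documents and will differ among the three endpoints. A reader might infer a large understatement; that would rest entirely on assumed prevalences, and at 5% the ratio is 1.05. The identity assumes that censoring is unrelated to baseline status. It applies cleanly to a prior pacemaker and to known AF. It applies to conduction delay only once the endpoint is defined and matched to a specific delay.

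This is a cheap improvement that serves the objective of supplying event rates for pivotal planning, in a descriptive study with no hypothesis at stake.

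**What to change.** In SAP 7.9.1, keep the all-attempted rates and add beside them, with both denominators shown:

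- **New pacemaker:** the Kaplan-Meier rate in subjects without a pacemaker at baseline.
- **New-onset AF:** the Kaplan-Meier rate in subjects without known AF, from history or the baseline ECG.
- **New conduction delay:** write the definition first, then take as at risk for each specific delay the subjects in whom that delay is absent on the baseline ECG.

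The cost is SAP wording, a smaller denominator and slightly wider limits. In the example with 15 subjects excluded, the interval widens from 15.4 points (21.8 − 6.4) to 18.7 points (26.8 − 8.1), partly because the rate itself is higher.

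One item needs checking. Protocol 6.6 requires a medical history and 12-lead ECG at baseline, but protocol 13.2 does not name rhythm or device history among the items to emphasize, and a single ECG would miss paroxysmal AF. The case report form must carry a baseline flag for prior pacemaker and for AF; if it does not, the flag has to be added.

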7.9.2 Efficacy Endpoints

7.9.2.1 Device success (VARC-2)

Device success is defined as meeting all of the following:

- Absence of procedural mortality, AND
- Correct positioning of a single prosthetic heart valve into the proper anatomical location, AND
- Absence of patient prosthesis-mismatch AND mean aortic valve gradient < 20 mmHg (or peak velocity < 3 m/sec), AND
- Absence of moderate or severe prosthetic valve regurgitation.

Components of device success will be reported on the procedure CRF, the echo core lab CRF at discharge, and CEC CRF:

- Procedural mortality will be defined as any death occurring within 30 days of implant or prior to hospital discharge.
- Correct positioning of the single prosthetic heart valve into the proper anatomical location will be reported by the investigator on the procedure CRF.
- Absence of patient-prosthesis mismatch will be derived from the echo core lab data at discharge. Patient prosthesis mismatch is defined in Section 7.9.2.4.
- Mean aortic valve gradient < 20 mmHg (or peak velocity < 3 m/sec) will be derived from the echo core lab CRF at discharge
- Absence of moderate or severe prosthetic valve regurgitation will be derived from the echo core lab CRF at discharge

The endpoint will be reported as the count and percentage of subjects achieving device success with two-sided 95% exact binomial confidence interval. Subjects will be defined as success if all components are met. Subjects will be defined as failure if any one component with available data is not met, regardless if data are available for all components. Subjects missing data for any components and not meeting criteria for failure will be considered to have a missing outcome. The numerator will include the number of subjects with device success and the denominator will include subjects evaluable for device success (known status of success or failure). The components of device success will also be summarized descriptively. The endpoint will be analyzed using the Implanted set.

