7.7 Clinical Events Committee

A Clinical Events Committee (CEC) will provide independent medical review and adjudication of adverse event data used in the safety assessment of the investigational device. The CEC will adjudicate, at minimum, all deaths and safety endpoint-related adverse events and TAVR related complications reported by the investigators, and may leverage core lab-reported data for events where echo imaging is used in the adjudication. The CEC will follow the VARC II⁶³ recommendations where relative for classifying adverse events related to clinical safety endpoints. The analysis of the study safety data will be based on CEC adjudicated events. Definitions of safety endpoints and other TAVR related complications are provided in Section 13.8.

The committee will consist of at least 3 independent experts (non-Medtronic employed physicians that are not participating investigators for the study) with expertise relevant to the study. This may include experience in the areas of:

- Interventional cardiology
- Cardiology
- Neurology
- Cardiac surgery

A CEC charter will be approved by Medtronic and the CEC prior to the first subject enrollment.

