13.7 Appendix VII: TAVR Implant Procedure

The implantation procedure is performed according to the standard procedures of the implanting physicians. Valve deployment in accordance with the cusp overlap technique⁶² is recommended for TAVR implant for all study subjects, as appropriate. Transfemoral access is required for the TAVR implant. For sites in the United States, the local heart team’s interventional cardiologist(s) and cardiac surgeon(s) must jointly participate in the intra-operative technical aspects of the TAVR procedure. Procedural aspects specific to the Medtronic TAVR system should be performed according to the Instructions for Use. TAV size selection should be based on MDCT measurements and the dimensional criteria shown in Figure 21.

Size	23 mm	26 mm	29 mm	34 mm
Annular perimeter	56.5 – 62.8 mm	62.8 – 72.3 mm	72.3 – 81.7 mm	81.7 – 94.2 mm
Annular diameter (mean)	18 – 20 mm	20 – 23 mm	23 – 26 mm	26 – 30 mm
Sinus of Valsalva diameter (mean)	≥ 25 mm	≥ 27 mm	≥ 29 mm	≥ 31 mm
Sinus of Valsalva height (mean)	≥ 15 mm	≥ 15 mm	≥ 15 mm	≥ 16 mm

Figure 21. TAV sizing matrix showing the anatomical dimensional criteria for each TAV size.

The following variables will be collected regarding the TAVR implantation procedure:

- Name of the primary operator
- Anesthesia type (general or local)
- Pre-implant pressures (LV systolic and end-diastolic, aortic systolic and diastolic)
- Pre-implant mean aortic gradient (simultaneous recording or LV and central aortic pressures)
- Pre-deployment BAV (yes/no)
- Use of rapid or controlled pacing during BAV and deployment (yes/no)

- Size of TAV implanted
- Post-implant dilation (yes/no)
- Implantation of TAV within the desired location (yes/no)
- Post-implant grade of prosthetic regurgitation by angiography (final result)
- More than one TAV implanted (yes/no)
- Patency of coronary arteries post-implant (yes/no)
- Occurrence of adverse events
- If TAV implantation not attempted, reason why

Criteria for grading prosthetic regurgitation by aortography⁸⁷

Grade 1+, mild: A small amount of contrast material enters the left ventricle in diastole; it is essentially cleared with each beat and never fills the ventricular chamber.

Grade 2+, moderate: More contrast material enters with each diastole and faint opacification of the entire chamber occurs.

Grade 3+, moderately severe: The left ventricle chamber is well opacified and equal in density with the ascending aorta.

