Valve migration: After initial correct positioning, any observed movement (upward or downward) of the TAV within the aortic annulus from its initial position, with or without consequences.

Valve embolization: The TAV moves during or after deployment such that it loses contact within the aortic annulus.

Ectopic valve deployment: Permanent deployment of the TAV in a location other than the aortic root.

TAV in TAV deployment: Additional valve prosthesis is implanted within a previously implanted TAV because of sub-optimal device position and/or function, during or after the index procedure.

Hemolysis: Red cell destruction confirmed by lab data; Minor hemolysis: No intervention required; Major hemolysis: Requires intervention (e.g. iron supplements, transfusion, invasive intervention).

Prosthetic Valve Endocarditis: Any of the following;

1) Fulfillment of the following Duke criteria for definite endocarditis:

- Histologic and/or microbiologic evidence of infection at surgery or autopsy, or
- 2 major criteria, or
- 1 major criteria or 3 minor criteria, or
- 5 minor criteria

Major Criteria:

- Blood cultures positive for Infective Endocarditis (IE)
 - Typical microorganisms consistent with IE isolated from two separate blood cultures, as noted below
 - Viridans streptococci, *Streptococcus bovis*, *Staphylococcus aureus*, or HACEK group
 - Community-acquired enterococci in the presence of a primary focus
 - Microorganisms consistent with IE isolated from persistently positive blood cultures defined as:
 - At least two positive cultures or blood samples obtained >12 hours apart, or
 - All of three, or a majority of four or more separate cultures of blood, the first and last sample obtained > one hour apart
 - Single blood culture positive for *Coxiella burnetii* or an antiphase I IG antibody titer >1:800
- Evidence of endocardial involvement
 - Positive results of echocardiography for IE defined as:
 - Oscillating intracardiac mass on a valve or supporting structures in the path of regurgitant jets or on implanted material in the absence of an anatomic explanation, or
 - Abscess, or
 - New partial dehiscence of a valvular prosthesis
 - New valvular regurgitation (worsening or changing or pre-existing murmur not sufficient)

Minor Criteria:

- Predisposition: predisposing heart condition or intravenous drug use
- Fever: temperature >38°C

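### Device success takes its single-valve position component only from the procedure CRF, so a subject whose valve embolises, or who gets a second TAV, before a good discharge echo can count as a success

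*SAP*

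**What the plan says.** Protocol 13.8.3 and SAP 7.9.2.1 both require a single prosthetic valve, correctly positioned, as one of the device-success components. The protocol gives that component no data source and no time point, so the SAP supplies the working rule.

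For the composite as a whole, the SAP states: "Components of device success will be reported on the procedure CRF, the echo core lab CRF at discharge, and CEC CRF". It then goes through the components:

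- **Mortality:** "Procedural mortality will be defined as any death occurring within 30 days of implant or prior to hospital discharge".
- **Position and single valve:** "Correct positioning of the single prosthetic heart valve into the proper anatomical location will be reported by the investigator on the procedure CRF".
- **Regurgitation:** "Absence of moderate or severe prosthetic valve regurgitation will be derived from the echo core lab CRF at discharge". Gradient and patient-prosthesis mismatch come from the same echo.

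A subject is a success if all components are met, and a failure if any component with data is not met. Protocol 13.7 lists the matching procedure items as two yes/no questions, one on desired location and one on more than one TAV, among the data about the implantation procedure. Protocol 6.6 puts the discharge echo between 12 hours and 7 days after the procedure.

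Protocol 13.8.2 defines valve embolization so that it covers later events: "The TAV moves during or after deployment such that it loses contact within the aortic annulus". TAV-in-TAV deployment is an added valve "because of sub-optimal device position and/or function, during or after the index procedure". Under Protocol 7.7, "The CEC will adjudicate, at minimum, all deaths and safety endpoint-related adverse events and TAVR related complications reported by the investigators".

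**The concern.** The components of one composite are read at different times. Mortality and the haemodynamic components look past the procedure, while position and valve count are read from a form about the procedure itself. Between that form and the echo there can be up to 7 days in which the first valve is lost or a second is added. If that happens and the echo is then good, the composite records a success for a subject who does not have one correctly placed valve.

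The study will hold adjudicated information on reported events of this kind, so the same subject could appear as a device success in one table and as a CEC-confirmed embolization or TAV-in-TAV in another. Estimating event rates for possible pivotal endpoints is a primary objective (Protocol 4.1). A reader planning the pivotal study would want the composite to mean what its definition says.

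**Working it through.** The plan gives no device-success rate or target, so there is no figure to reproduce. The check traces each component to its source, then sizes one misclassified subject.

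**Step 1. Source and time of each component (SAP 7.9.2.1; Protocol 6.6 and 13.7)**

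| Component | Source | Read at |
|---|---|---|
| Procedural mortality | CEC CRF (inferred; the SAP assigns that form to no named component) | 30 days or hospital discharge |
| Position, single valve | Investigator, procedure CRF | No time stated; items describe the procedure |
| Gradient, mismatch, regurgitation | Core-lab echo | 12 hours to 7 days |

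**Step 2. Apply the rule to constructed cases**

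- *Second TAV during the index procedure.* The item on more than one TAV is answered yes. Caught.
- *Correct placement on day 0; embolization or second TAV on day 2; good echo of the second valve on day 5; subject survives.* The procedure CRF shows correct location and one valve, the echo components are met, and mortality is met. Counted as a **success**. Not caught.
- *The same events, but no discharge echo.* No component with data fails, so the outcome is missing rather than failure.
- *Embolization left uncorrected.* The echo would be expected to fail on gradient or regurgitation. Probably caught.
- *Migration with no haemodynamic effect.* Counted as a success. This agrees with the protocol's own vocabulary, which defines migration as movement following a correct initial placement. Not an error.

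**Step 3. Size per subject**

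1/75 = 1.33 points. At the initial analysis with 50 subjects, 1/50 = 2.0 points.

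The intervals below are Clopper-Pearson, the exact binomial method that the SAP names. The starting rate of 96% is only an illustration.

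| Subjects reclassified | N = 75 | N = 50 |
|---|---|---|
| 0 | 72/75 = 96.0% (88.8 to 99.2) | 48/50 = 96.0% (86.3 to 99.5) |
| 1 | 71/75 = 94.7% (86.9 to 98.5) | 47/50 = 94.0% (83.5 to 98.7) |
| 2 | 70/75 = 93.3% (85.1 to 97.8) | 46/50 = 92.0% (80.8 to 97.8) |

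The first interval at N = 75 is 99.2 − 88.8 = 10.4 points wide, so a shift of one or two subjects lies well inside it.

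**Step 4. How likely is at least one such subject?**

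The documents give no rate. For an assumed probability p per subject, the chance of at least one among 75 is 1 − (1 − p)^75:

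- p = 0.5%: 31%, expected number 75 × 0.005 = 0.4
- p = 1%: 53%, expected number 0.75
- p = 3%: 90%, expected number 75 × 0.03 = 2.3

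This range is assumed, and zero events is possible.

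**The case against.** The best reply is that positioning means the act of placement, for which the procedure CRF is a natural source. The CRF and its completion rules are also not among the documents. Protocol 12.3 asks for eCRFs to be kept up to date with the latest observations, and Protocol 13.8.4 mentions a re-implant procedure, so a day-2 second valve might be entered on a procedure form after all. This has some weight, but it does not settle the matter. The general updating sentence does not say that procedure items are re-answered for later events, and the SAP gives the component no time point. The CEC CRF is named for the composite but is not tied to position.

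It is also fair to say that these events are not lost. A repeat procedure for valve dysfunction is a CEC-adjudicated safety endpoint, and the CEC reviews reported TAVR complications. Only the composite misses them. Since the CEC works from what investigators report, using its data does not make detection independent of the sites.

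A reader might be tempted by four stronger readings, none of which the documents support:

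- *Silent migration should fail the component.* Under Protocol 13.8.2, migration presupposes correct initial positioning and may be without consequences. Failing those subjects would change the endpoint.
- *Ectopic deployment is likewise defined to include later events.* Its definition has no such wording; only those of embolization and TAV-in-TAV do.
- *The implanting operator grades their own work.* The SAP says investigator, and Protocol 5.5.1 allows a principal investigator who does not implant.
- *The rule breaks Protocol 10.8.* That section commits the CEC to deaths and safety endpoint events, and the core lab to echo endpoints. It promises no independent review of valve position.

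**Conclusion.** The point holds in a narrow form. As SAP 7.9.2.1 is written, a subject with embolization or a second TAV between the index procedure and a satisfactory discharge echo can be counted as a device success, and the planned CEC adjudication of that event plays no part. Relative to a rule that used the adjudication, the misclassification can only raise the rate.

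The effect is 1.3 points per subject at N = 75, or 2.0 at N = 50. This rests on two assumptions: that at least one such event occurs, for which the documents give no rate, and that the procedure CRF is not re-answered for later events, which cannot be checked without the form.

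The priority is low. The study has no hypotheses, device success has no threshold, and it is absent from the key endpoint lists in the Protocol Synopsis and SAP section 4. Its place as first in the list of efficacy endpoints is order, not rank.

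**What to change.** Replace the positioning sentence in SAP 7.9.2.1 with:

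> *The positioning component is not met if the investigator reports an incorrect location or more than one TAV on the procedure CRF, or if the CEC adjudicates valve embolization or TAV-in-TAV deployment with onset from the index procedure up to the discharge echo (up to day 7 if that echo is missing).*

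Report migration separately, and show the procedure-CRF-only version as one of the listed components so that both readings are visible. The new cut-off matches the haemodynamic components; mortality still runs to 30 days, as now. If the component is instead meant to be intraprocedural only, the SAP should say so, and the reader can then interpret the rate accordingly.

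The cost is one SAP sentence and a merge with CEC data already planned. No new data are collected. The downside is a device-success rate that may be slightly lower. A subject with a CEC-confirmed event and no discharge echo would also move from missing to failure, under the SAP's existing rule that one failed component is enough.
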